Appendix 7: Hepatotoxicity Stopping Rules: Suggested Actions and Follow-up Assessments

Subjects with abnormal hepatic laboratory values (i.e., alkaline phosphatase [ALP], aspartate aminotransferase [AST], alanine aminotransferase [ALT], total bilirubin [TBL]) and/or international normalized ratio (INR) and/or signs/symptoms of hepatitis (as described below) may meet the criteria for withholding or permanent discontinuation of Amgen investigational product or other protocol-required therapies, as specified in the Guidance for Industry Drug-Induced Liver Injury: Premarketing Clinical Evaluation, July 2009.

Criteria for Withholding and/or Permanent Discontinuation of Amgen Investigational Product and Other Protocol-required Therapies Due to Potential Hepatotoxicity

The following stopping and/or withholding rules apply to subjects for whom another cause of their changes in liver biomarkers (TBL, INR, and transaminases) has not been identified.

Important alternative causes for elevated AST/ALT and/or TBL values include, but are not limited to:

- Hepatobiliary tract disease
- Viral hepatitis (e.g., hepatitis A/B/C/D/E, Epstein-Barr Virus, cytomegalovirus, herpes simplex virus, varicella, toxoplasmosis, and parvovirus)
- Right-sided heart failure, hypotension, or any cause of hypoxia to the liver causing ischemia
- Exposure to hepatotoxic agents/drugs or hepatotoxins, including herbal and dietary supplements, plants, and mushrooms
- Heritable disorders causing impaired glucuronidation (e.g., Gilbert's syndrome, Crigler-Najjar syndrome) and drugs that inhibit bilirubin glucuronidation (e.g., indinavir, atazanavir)
- Alpha-one antitrypsin deficiency
- Alcoholic hepatitis
- Autoimmune hepatitis
- Wilson's disease and hemochromatosis
- Nonalcoholic fatty liver disease including steatohepatitis
- Non-hepatic causes (e.g., rhabdomylosis, hemolysis).

If investigational product(s) is/are withheld, the subject is to be followed for possible drug-induced liver injury (DILI) according to recommendations in the last section of this appendix.

Rechallenge may be considered if an alternative cause for impaired liver tests (ALT, AST, ALP) and/or elevated TBL is discovered and the laboratory abnormalities resolve to normal or baseline (see next section in this appendix).

Table 2: Conditions for Withholding and/or Permanent Discontinuation of Amgen Investigational Product and Other Protocol-required Therapies Due to Potential Hepatotoxicity

Analyte	Temporary Withholding	Permanent Discontinuation
TBL	>3x ULN at any time	>2x ULN
INR	--	>1.5x (for subjects not on anticoagulation therapy)
	OR	AND
AST/ALT	>8x ULN at any time >5x ULN but <8x ULN for ≥2 weeks >5x ULN but <8x ULN and unable to adhere to enhanced monitoring schedule >3x ULN with clinical signs or symptoms that are consistent with hepatitis (such as right upper quadrant pain/tenderness, fever, nausea, vomiting, and jaundice)	In the presence of no important alternative causes for elevated AST/ALT and/or TBL values >3x ULN (when baseline was < ULN)
	OR	
ALP	>8x ULN at any time	--

Abbreviations: ALP = alkaline phosphatase; ALT = alanine aminotransferase; AST = aspartate aminotransferase; INR = international normalized ratio; TBL = total bilirubin; ULN = upper limit of normal.

Criteria for Rechallenge of Amgen Investigational Product and Other Protocol-required Therapies After Potential Hepatotoxicity

The decision to rechallenge the subject is to be discussed and agreed upon unanimously by the subject, Investigator, and Amgen.

If signs or symptoms recur with rechallenge, then sotorasib is to be permanently discontinued.

Subjects who clearly meet the criteria for permanent discontinuation (as described in [Table 2](#)) are never to be rechallenged.

Drug-induced Liver Injury Reporting and Additional Assessments

Reporting

To facilitate appropriate monitoring for signals of DILI, cases of concurrent AST or ALT and TBL and/or INR elevation, according to the criteria specified above, require the following:

- The event is to be reported to Amgen as a serious adverse event within 24 hours of discovery or notification of the event (i.e., before additional etiologic investigations have been concluded).
- The appropriate electronic Case Report Form (eCRF) that captures information necessary to facilitate the evaluation of treatment-emergent liver abnormalities is to be completed and sent to Amgen.

Other events of hepatotoxicity and potential DILI are to be reported as serious adverse events if they meet the criteria for a serious adverse event defined in [Appendix 1](#).

Additional Clinical Assessments and Observation

All subjects in whom investigational product(s) or protocol-required therapies is/are withheld (either permanently or conditionally) due to potential DILI as specified in [Table 2](#) or who experience AST or ALT elevations >3 x upper limit of normal (ULN) or 2-fold increases above baseline values for subjects with elevated values before drug are to undergo a period of “close observation” until abnormalities return to normal or to the subject’s baseline levels.

Assessments that are to be performed during this period include:

- Repeat AST, ALT, ALP, bilirubin (BIL; total and direct), and INR within 24 hours
- In cases of TBL >2 x ULN or INR >1.5 , retesting of liver tests, BIL (total and direct) and INR is to be performed every 24 hours until laboratory abnormalities improve.

Testing frequency of the above laboratory tests may decrease if the abnormalities stabilize or the investigational product(s) or protocol-required therapies has/have been discontinued AND the subject is asymptomatic.

Initiate investigation of alternative causes for elevated AST or ALT and/or elevated TBL.

The following are to be considered depending on the clinical situation:

- Complete blood count with differential to assess for eosinophilia
- Serum total immunoglobulin G, anti-nuclear antibody anti-smooth muscle antibody, and liver kidney microsomal antibody-1 to assess for autoimmune hepatitis
- Serum acetaminophen (paracetamol) levels

- A more detailed history of:
 - Prior and/or concurrent disease or illness
 - Exposure to environmental and/or industrial chemical agents
 - Symptoms (if applicable) including right upper quadrant pain, hypersensitivity-type reactions, fatigue, nausea, vomiting, and fever
 - Prior and/or concurrent use of alcohol, recreational drugs, and special diets
 - Concomitant use of medications (including nonprescription medicines and herbal and dietary supplements), plants, and mushrooms
- Viral serologies
- Creatine phosphokinase, haptoglobin, lactate dehydrogenase, and peripheral blood smear
- Appropriate liver imaging if clinically indicated
- Appropriate blood sampling for pharmacokinetic analysis, if this has not already been collected
- Hepatology consult (liver biopsy may be considered in consultation with a hepatologist).

Follow the subject and the laboratory tests (ALT, AST, TBL, INR) until all laboratory abnormalities return to baseline or normal or considered stable by the Investigator. The “close observation period” is to continue for a minimum of 4 weeks after discontinuation of all investigational product(s) and protocol-required therapies.

The potential DILI event and additional information such as medical history, concomitant medications, and laboratory results must be captured in the corresponding eCRFs.

Appendix 8: Schedule of Assessments

Schedule of Assessments

Study Procedures	Screening	Check-in	Rosuvastatin					Rosuvastatin in Combination with Sotorasib					Day 11 (EOS/ ET)
	Day -21 to Day -2	Day -1	Day 1	Day 2	Day 3	Day 4	Day 5	Day 6	Day 7	Day 8	Day 9	Day 10	
Confined to the CRU		X	X	X	X	X	X	X	X	X	X	X	X
Outpatient Visit	X												
Inclusion/Exclusion Criteria	X	X											
Informed Consent	X												
Demographics	X												
Serology	X												
Medical History	X	X ^a											
Height and BMI	X												
Weight	X	X											X ^o
Drug Screen	X	X											
Alcohol Urine Test	X	X											
Pregnancy Test (females only) ^b	X	X											X ^o
FSH (postmenopausal females only)	X												
12-lead Electrocardiogram ^c	X	X											
Vital Signs ^d	X	X	X	X	X			X	X	X			X ^o
Clinical Laboratory Evaluations ^e	X	X					X						X ^o
eGFR ^f	X	X				X							
Physical Examination ^g		X					X						X ^o
Rosuvastatin Dose ^h			X				X						
Sotorasib Dose ⁱ							X						
Rosuvastatin PK Blood Samples ^j			X	X	X	X	X	X	X	X	X	X	X
Sotorasib PK Blood Samples ^k								X	X	X			
Adverse Event Monitoring ^l								X					
Serious Adverse Event Monitoring ^l	X							X					
Prior/Concomitant Medications ^m	X							X					

Abbreviations: BMI = body mass index; CRU = Clinical Research Unit; eGFR = estimated glomerular filtration rate; EOS = end of study; ET = early termination;

FSH = follicle-stimulating hormone; PK = pharmacokinetic.

^a Interim medical history only.

^b Performed in serum at Screening and in urine at all other times. A positive urine pregnancy test will be confirmed with a serum pregnancy test.

^c Electrocardiograms will be collected after the subject has rested in the supine position for at least 5 minutes, and will be obtained prior to the scheduled blood draws.

^d Vital signs measurements (supine blood pressure [BP], supine heart rate, respiratory rate, and oral body temperature) should be carried out prior to having blood drawn. Screening; Check-in; prior to rosuvastatin administration on Days 1 and 6; 1, 24, and 48 hours following rosuvastatin administration on Days 1 and 6; and EOS/ET. Heart rate and BP will be measured using the same arm for each reading after the subject has been resting in the supine position for at least 5 minutes.

^e Clinical chemistry (fasted at least 8 hours), hematology, and urinalysis.

^f eGFR will be calculated using the Modification of Diet in Renal Disease equation.

^g A full physical examination at Check-in and a symptom-directed physical examination on Day 6 and at EOS/ET.

^h Dose administration of rosuvastatin is to occur during the mornings of Days 1 and 6 following an overnight fast of at least 10 hours. On Day 6, rosuvastatin administration will occur immediately after administration of sotorasib.

ⁱ Dose administration of sotorasib is to occur during the morning of Day 6 following an overnight fast of at least 10 hours.

^j Blood samples for determination of rosuvastatin plasma concentrations and PK parameters will be collected: Predose (Hour 0), 0.5, 1, 2, 3, 4, 5, 6, 8, 10, 12, 24, 36, 48, 72, 96, and 120 hours postdose following administration of rosuvastatin on Days 1 and 6.

^k Blood samples for determination of sotorasib plasma concentrations and PK parameters will be collected: Predose (Hour 0), 0.5, 1, 2, 3, 4, 5, 6, 8, 10, 12, 24, 36, and 48 hours postdose following administration of sotorasib on Day 6. The PK sample collected 30 minutes postdose will have a sampling window of \pm 2 minutes, samples collected from 1 through 3 hours postdose will have a sampling window of \pm 5 minutes, samples collected from 4 through 10 hours postdose will have a sampling window of \pm 10 minutes, and samples collected from 12 through 48 hours postdose will have a sampling window of \pm 20 minutes. Times of all PK samples will be recorded to the nearest minute.

^l Adverse events will be recorded from initiation of study treatment on Day 1 until EOS completion. Serious adverse events will be recorded from the time the subject signs the informed consent form through 30 days after the last dose of study treatment or the EOS (whichever is later).

^m Prior and concomitant medication administration will be recorded beginning at informed consent. In addition, all Investigator-approved medications taken by a subject within 30 days or 5 half-lives (whichever is longer) prior to enrollment administration for over-the-counter or prescription medications, and 30 days prior to enrollment for herbal medicines (e.g., St. John's wort), vitamins, and supplements, will be recorded on the subject's electronic Case Report Form.

ⁿ Performed prior to dosing.

^o Assessment to be performed at the EOS visit or if a subject is withdrawn early from the study.

1. INTRODUCTION

This SAP has been developed after review of the clinical study protocol (Final Version 1.0 dated 19 May 2021) and electronic case report form (eCRF).

This SAP describes the planned analysis of the pharmacokinetic (PK), safety, and tolerability data from this study. A detailed description of the planned TFLs to be presented in the clinical study report (CSR) is provided in the accompanying TFL shells document.

In general, the analyses are based on information from the protocol, unless they have been modified by agreement with Amgen Inc. A limited amount of information about this study (eg, objectives, study design) is given to help the reader's interpretation.

This SAP must be finalized prior to the lock of the clinical database. Additionally, the SAP and TFL shells should be finalized prior to any programming activities commencing.

This SAP supersedes any statistical considerations identified in the protocol; where considerations are substantially different, they will be so identified. If additional analyses are required to supplement the planned analyses described in this SAP, they may be performed and will be identified accordingly in the CSR. Any substantial deviations from this SAP will be agreed with Amgen Inc. and identified in the CSR.

This SAP is written with consideration of the recommendations outlined in the International Conference on Harmonisation (ICH) E3 guideline *Structure and Content of Clinical Study Reports*, ICH E8 guideline *General Considerations for Clinical Trials*, ICH E9 guideline *Statistical Principles for Clinical Trials*.^{1,2,3}

The document history is presented in Appendix 1.

2. STUDY OBJECTIVES

The primary objective of the study is:

• to determine the effect of sotorasib on the PK of rosuvastatin, and to assess the PK of rosuvastatin when administered alone, in healthy subjects.

The secondary objectives of the study are:

- to assess the safety and tolerability of sotorasib when coadministered with rosuvastatin, and rosuvastatin alone, in healthy subjects
- to assess the PK of sotorasib when coadministered with rosuvastatin.

3. STUDY ENDPOINTS

The primary endpoints of the study are rosuvastatin PK parameters:

• maximum observed concentration (C_{max})

Page 7 of 23

- area under the concentration-time curve (AUC) from time zero to the last quantifiable concentration (AUC_{last})
- area under the concentration-time curve from time zero to infinity (AUC_{inf}).

The secondary endpoints of the study are:

- adverse events (AE)
- clinical laboratory tests
- 12-lead electrocardiograms (ECGs)
- vital signs
- sotorasib PK parameters after administration of sotorasib in combination with rosuvastatin, including, but not limited to:
 - \circ C_{max}
 - o AUC_{last}
 - o AUCinf.

4. STUDY DESIGN

This will be a Phase I, open-label, fixed sequence, crossover study to investigate the effect of coadministration of sotorasib on the PK of rosuvastatin in healthy male subjects and healthy female subjects of nonchildbearing potential. Approximately 14 subjects will be enrolled to ensure that 12 subjects complete the study. All subjects will receive each of the following treatments:

- Day 1: single oral dose of 10 mg rosuvastatin (1 x 10 mg tablet), after an overnight fast of at least 10 hours
- Day 6: single oral dose of 960 mg sotorasib (8 x 120 mg tablets) followed immediately by a single oral dose of 10 mg rosuvastatin (1 x 10 mg tablet), after an overnight fast of at least 10 hours.

Potential subjects will be screened to assess their eligibility to enter the study within 21 days prior to the first dose administration. Subjects will be admitted into the Clinical Research Unit (CRU) on Day -1 and be confined to the CRU until discharge on Day 11.

The total duration of study participation for each subject (from Screening through end of study discharge) is anticipated to be approximately 4 and a half weeks.

[figure not shown]
The start of the study is defined as the date the first enrolled subject signs an Informed Consent Form (ICF). The point of enrollment occurs at the time of subject number allocation.

SAP CONFIDENTIAL Covance Study: 8461525 Protocol Reference: 20200426

The end of the study is defined as the date of the last subject's last assessment (scheduled or unscheduled).

An overview of the study design is shown in Figure 1.

Figure 1: Study Design

5. SAMPLE SIZE JUSTIFICATION

Approximately 14 subjects will be enrolled in order that approximately 12 subjects complete the study. The sample size for this study is based on studies of similar design and considered adequate for evaluation of the study objectives.

6. STUDY TREATMENTS

The study treatment names, abbreviations, and ordering to be used in the TFLs are presented in **Error! Not a valid bookmark self-reference.**

Table 1: Presentation of Study Treatments in TFLs

Treatments	Abbreviation	Order in TFLs
single oral dose of 10 mg rosuvastatin (1 x 10 mg tablet), after an overnight fast of at least 10 hours	10 mg rosuvastatin	1
single oral dose of 960 mg sotorasib (8 x 120 mg tablets) followed immediately by a single oral dose of 10 mg rosuvastatin (1 x 10 mg tablet), after an overnight fast of at least 10 hours	960 mg sotorasib + 10 mg rosuvastatin	2

7. DEFINITIONS OF POPULATIONS

Any protocol deviations, including those due to coronavirus disease 2019 (COVID-19) and related restrictions (see Section 8.1.1), will be considered prior to database lock for their importance and taken into consideration when assigning subjects to populations.

7.1. All Subjects Population

The All Subjects Population will include all subjects who signed the ICF and had any study assessment recorded in the database per the protocol.

7.2. Safety Population

The Safety Population will include all subjects who received at least 1 dose of sotorasib or rosuvastatin and have at least 1 postdose safety assessment.

7.3. Pharmacokinetic Population

The PK population will include all subjects who received at least 1 dose of rosuvastatin or sotorasib and have evaluable PK data. A subject may be excluded from the PK summary statistics and statistical analysis if the subject has an adverse event of vomiting that occurs at or before 2 times median time to maximum concentration or diarrhea within 24 hours of dosing.

8. STATISTICAL METHODOLOGY

8.1. General

Listings will be provided for all data captured in the database, with the exception of medical history. Listings will include all subjects assigned to the All Subjects Population and include data up to the point of study completion or discontinuation. Subjects are generally considered to have completed the study if they complete the scheduled end of study visit (rather than early termination visit). Any subject who discontinues the study will be identified accordingly in the listings. Summaries and statistical analyses will include the subjects assigned to the relevant population based on data type.

Data analysis will be performed using the SAS® statistical software package Version 9.4 (or higher if a new version is issued during the study).

Analysis Data Model (ADaM) datasets will be prepared using Clinical Data Interchange Standards Consortium (CDISC) ADaM Version 2.1 (or higher if a new version is issued during the study) and CDISC ADaM Implementation Guide Version 1.1 (or higher if a new version is issued during the study). Pinnacle 21 Enterprise Version 4.2.1 (or higher if a new version is issued during the study) will be utilized to ensure compliance with CDISC standards.

Caution should be used when interpreting results from the statistical analyses conducted in this study because the sample size is not based on power calculations.

Where reference is made to 'valid' data, this refers to non-missing data which meet the predetermined criteria (eg, are not flagged for exclusion).

Where reference is made to 'all calculations', this includes, but is not limited to, summary statistics, statistical analyses, baseline derivation, changes from baseline, percentage changes from baseline, and any parameter derivations.

All figures will be produced on linear-linear or discrete-linear scales, as applicable, unless specifically stated otherwise.

8.1.1. Handling of Data Quality Issues Due to Coronavirus Disease 2019 and Related Restrictions

Due to COVID-19 and related restrictions, there is a high risk for impact to data integrity, with the recognized potential for:

- Missed visits, caused by, for example:
 - Subject unable to travel to site due to restrictions, the need to quarantine, or COVID-19 infection
 - o Subject unwilling to go to site due to fear of COVID-19 infection
 - Site postponing subject's visit due to investigator not being available (eg, if they have been dispatched to hospital handling COVID-19 infections)
- Site unable to replenish supply of investigational product
- Incomplete data entry by sites due to limited resources to support study or no access to source documents or to eCRF
- Outstanding source document verification (SDV) due to sponsor or country restrictions on remote SDV, or no or limited access to site(s) for on-site visits
- Unanswered queries

At the time of the reporting of the study results, all protocol deviations due to COVID-19 or related restriction will be assessed for their severity and impact on the analyses. If needed, appropriate statistical methods will be applied as a mitigating action (eg, data might be categorized into 2 analysis groups, with and without COVID-19 and related restrictions impact); however, this will exclude any imputations of the missing values. Any mitigating actions will be agreed with Amgen Inc. in advance and identified in the CSR.

8.1.2. Calculation of the Summary Statistics

For continuous data the following rules will be applied:

• Missing values will not be imputed, unless specifically stated otherwise.

- Unrounded data will be used in the calculation of summary statistics.
- If the number of subjects with valid observations (n) <3, summary statistics will not be calculated, with the exception of n, minimum, and maximum.
- In general, as early termination data are not associated with any scheduled timepoint, they will be excluded from all calculations of summary statistics and statistical analyses. Exceptions may be made where justified.

For categorical data the following rules will be applied:

- For ordered categorical data (eg, AE severity), all categories between the possible minimum and maximum categories will be included, even if n = 0 for a given category.
- For non-ordered categorical data (eg, race), only those categories for which there is at least 1 subject represented will be included; unless specifically stated otherwise.
- Missing values will not be imputed, unless specifically stated otherwise. A 'missing' category will be included for any parameter for which information is missing. This will ensure that the population size totals are consistent across different parameters.

8.1.3. Repeat and Unscheduled Readings

For vital signs and 12-lead ECG data only, any predose value recorded in addition to the original value or a postdose value recorded within 15 minutes of the original value will be defined as a repeat value; any postdose value recorded more than 15 minutes after the original value will be defined as an unscheduled value. For all other data types (eg, laboratory parameters), any value recorded in addition to the original value will be defined as an unscheduled value.

The original value will be replaced by the last associated repeat value in all calculations, with the exception of the 12-lead ECG outlier analysis (see Section 8.6.4).

As unscheduled values are not associated with any scheduled timepoint, they will be excluded from all calculations, with the exception of the baseline derivation (see Section Error! Reference source not found.) and 12-lead ECG outlier analysis (see Section 8.6.4).

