4.2. Exclusion Criteria

Subjects will be excluded from the study if they satisfy any of the following criteria prior to enrollment, unless otherwise stated:

1. History or evidence, at Screening or Check-in, of clinically significant disorder, condition, or disease, including history of myolysis, not otherwise excluded that, in the opinion of the Investigator (or designee), would pose a risk to subject safety or interfere with the study evaluation, procedures, or completion.
2. History or evidence of clinically significant arrhythmia at Screening, including any clinically significant findings on the ECG taken at Check-in.
3. A QT interval corrected for heart rate (HR) based on the Fridericia method (QTcF) interval >450 ms in male subjects or >470 ms in female subjects or history/evidence of long QT syndrome, at Screening or Check-in, confirmed by calculating the mean of the original value and 2 repeats.
4. PR interval >200 ms, second-degree atrioventricular (AV) block or third-degree AV block, at Screening or Check-in.
5. Systolic blood pressure (BP) >140 mmHg or <90 mmHg, or diastolic BP >90 mmHg, or HR >100 bpm, at Screening or Check-in. Subjects with out-of-range values that are not clinically significant (as determined by the Investigator) may have the test repeated once during Screening (within 1 hour of original assessment) and the subject may be enrolled if a repeated value is within normal range.
6. History suggestive of esophageal (including esophageal spasm, esophagitis), gastric, or duodenal ulceration or bowel disease (including, but not limited to, peptic ulceration, gastrointestinal bleeding, ulcerative colitis, Crohn's disease, or irritable bowel syndrome); or a history of gastrointestinal surgery other than uncomplicated appendectomy.
7. Inability to swallow oral medication or history of malabsorption syndrome.
8. History of hypersensitivity, intolerance, or allergy to any drug compound, food, or other substance, unless approved by the Investigator (or designee) and in consultation with the Sponsor.
9. Poor peripheral venous access.

10. Estimated glomerular filtration rate less than 70 mL/min/1.73 m² as calculated by the Modification of Diet in Renal Disease equation, at Screening or Check-in.

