7.2.3. Vital Signs

Supine BP, supine heart rate, respiratory rate, and oral body temperature will be assessed at the times indicated in the Schedule of Assessments in [Appendix 8](#). Vital signs may also be performed at other times if judged to be clinically appropriate or if the ongoing review of the data suggests a more detailed assessment of vital signs is required.

All measurements will be performed singly and repeated once if outside the relevant clinical reference range.

Subjects must be supine for at least 5 minutes before BP and pulse rate measurements. When vital signs are scheduled at the same time as blood draws, the blood draws will be obtained at the scheduled timepoint, and the vitals will be obtained as close to the scheduled blood draw as possible, but prior to the blood draw.

7.2.4. 12-lead Electrocardiogram

Resting 12-lead ECGs will be recorded after the subject has been supine and at rest for at least 5 minutes at the times indicated in the Schedule of Assessments in [Appendix 8](#). Single 12-lead ECGs will be repeated twice, and an average taken of the 3 readings, if either of the following criteria apply:

- QTcF is >500 ms
- QTcF change from the baseline (predose) is >60 ms.

Additional 12-lead ECGs may be performed at other times if judged to be clinically appropriate or if the ongoing review of the data suggests a more detailed assessment of ECGs is required. The Investigator (or designee) will perform a clinical assessment of each 12-lead ECG.

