8.6.3. Vital Signs Parameters

All vital signs parameters will be listed, as applicable; any value outside the clinical reference range will be flagged.

Summary tables and boxplots by treatment and timepoint will be provided by treatment group for all vital signs parameters as applicable.

8.6.4. 12-lead Electrocardiogram Parameters

All 12-lead ECG parameters will be listed; any value outside the clinical reference range will be flagged.

Summary tables by timepoint will be provided for all 12-lead ECG parameters.

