10. SIGNIFICANT CHANGES FROM THE PROTOCOL-SPECIFIED ANALYSES

There were no significant changes from the protocol-specified analyses.

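### Does it matter that SAP 8.1.3 tabulates the last repeat of an ECG, when the protocol averages the three readings, and cites an ECG outlier analysis that does not exist?

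*SAP*

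**What the plan says.** **Protocol.** Section 7.2.4 sets a rule for triggered ECGs: "Single 12-lead ECGs will be repeated twice, and an average taken of the 3 readings". The triggers are QTcF above 500 ms or a change of more than 60 ms from the predose baseline. Exclusion criterion 3 (Section 4.2) sets the QTcF limits at 450 ms for men and 470 ms for women at Screening or Check-in, "confirmed by calculating the mean of the original value and 2 repeats". Section 8.4 asks only that ECG endpoints be summarized.

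**SAP.** Section 8.1.3 treats any additional predose ECG as a repeat, and a postdose ECG as a repeat if it falls within 15 minutes of the original. It then directs: "The original value will be replaced by the last associated repeat value in all calculations, with the exception of the 12-lead ECG outlier analysis". Section 8.1 explains the scope of that phrase: "this includes, but is not limited to, summary statistics, statistical analyses, baseline derivation, changes from baseline". Section 8.1.3 names an ECG outlier analysis twice and points to Section 8.6.4. That section plans two outputs: "All 12-lead ECG parameters will be listed; any value outside the clinical reference range will be flagged" and "Summary tables by timepoint will be provided for all 12-lead ECG parameters". Section 10 states: "There were no significant changes from the protocol-specified analyses".

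**The concern.** Two documents appear to give different instructions for the same reading. A subject whose first QTcF is above the limit could be enrolled on the mean of three readings and then appear in the tables with the third reading alone. The SAP takes precedence over the protocol on statistical matters, but Section 1 adds that "where considerations are substantially different, they will be so identified", and Section 10 identifies nothing. ECGs are a named secondary endpoint, so a mismatch deserves a look.

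The missing outlier analysis looks worse at first sight. Section 8.1.3 keeps unscheduled ECGs out of every calculation except baseline derivation and that analysis. If the analysis does not exist, an extra ECG taken after dosing for clinical reasons would reach the listings only.

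**Working it through.** No figure in either document depends on this point, so there is none to reproduce. The check asks which ECG values the two rules could treat differently, and by how much.

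**Step 1: which ECGs are scheduled.** In the Schedule of Assessments (Protocol Appendix 8), the ECG row is marked at Screening and Check-in only. The ECG footnote gives no postdose times, whereas the vital-signs footnote gives 1, 24 and 48 hours. With 14 subjects there are 14 × 2 = 28 scheduled values, all before the first dose.

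**Step 2: can the 7.2.4 triggers reach a tabulated value?**

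- *Change above 60 ms.* This needs an ECG later than the predose baseline. None is scheduled. An extra postdose ECG is an unscheduled value and enters no summary table under either rule.
- *QTcF above 500 ms.* To remain eligible after such a reading, the mean of three must be at or below the limit. The two repeats must then average no more than (3 × 450 − 500)/2 = 425 ms for a man, or (3 × 470 − 500)/2 = 455 ms for a woman. That is a drop of at least 75 or 45 ms within one visit.
- *How often would a first reading exceed 500 ms?* Assume a mean of 415 ms, between-subject SD 17 ms and reading SD 10 ms (none of these is in the documents). The total SD is √(17² + 10²) = 19.7 ms and z = (500 − 415)/19.7 = 4.31. The probability is about 0.000008, or about 0.0002 expected values of 28, before the eligibility condition is applied.

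**Step 3: the values criterion 3 could touch.** These have a first reading above the limit, a mean of three within it, and a subject who is enrolled. They were simulated with three independent readings per visit and the criterion applied at both visits. Results are for reading SDs of 5 / 8 / 10 ms:

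| Assumed mean QTcF | Limit applied to all | Expected affected values of 28 |
|---|---|---|
| 415 ms | 450 ms | 0.16 / 0.34 / 0.49 |
| 415 ms | 470 ms | 0.01 / 0.03 / 0.05 |
| 425 ms | 450 ms | 0.41 / 0.77 / 1.05 |
| 425 ms | 470 ms | 0.05 / 0.11 / 0.18 |

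**Step 4: the size of the difference in an affected value.** For mean 415 and limit 450, the last repeat and the mean of three differ by 3.9 / 6.3 / 7.8 ms on average in absolute terms. One such value moves a visit mean over 14 subjects by 3.9/14 = 0.28 ms to 7.8/14 = 0.56 ms.

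**Step 5: is either rule the better estimate?** Same setting (mean 415, limit 450):

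| | Last repeat | Mean of three |
|---|---|---|
| Bias, all first readings above 450 ms | 0.0 / 0.0 / 0.0 ms | +1.1 / +2.6 / +3.7 ms |
| Root mean square error, same set | 5.0 / 8.0 / 10.0 ms | 3.1 / 5.2 / 6.7 ms |
| Bias, enrolled subjects' affected values only | −1.6 / −2.2 / −2.5 ms | +1.3 / +2.6 / +3.5 ms |

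The mean of three has the smaller error but keeps the high first reading that triggered the repeats. The last repeat is noisier and is unbiased until the eligibility selection acts. Neither rule is a mistake.

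**Step 6: the outlier analysis.** Section 8.6.4 gives no categories, thresholds or table for it. Its only role in 8.1.3 is as an exception to two handling rules, so with no such analysis the exceptions are empty. The listings still show every ECG, with out-of-range values flagged.

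**The case for a change.** The best case for a change is that agreement between documents is worth having for its own sake. The endpoint is named in both documents, the edit would be one sentence and two deletions, and the mean of three has the lower error. A programmer who reads both documents meets two rules, and Section 10 reports no departure. The schedule is also awkward to rely on: the table as read has shifted columns in places, so an ECG cell could have been lost, and a scheduled postdose ECG would make the 60 ms trigger possible.

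What stands is that the wording differs and the cross-references lead nowhere. What does not stand is that this leaves the analyst unsure or puts a result at risk. The SAP governs tabulation and gives one workable rule. The averaging text sits in the protocol's assessment section, while the protocol's safety analysis asks only for summaries. A difference this small need not count as substantial under SAP Section 1. The mean-of-three wording would also need more than the protocol supplies, because it gives no rule when a discretionary ECG yields one repeat or more than two. If a postdose ECG is in fact scheduled, the difference would arise only after a very large QTcF change. The individual readings would still be listed, and no inferential ECG analysis is planned.

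**Conclusion.** No change is needed. The last-repeat rule and the mean of three are both defensible, and the choice affects at most a few descriptive pre-treatment values. In the base case fewer than 0.5 of 28 values are expected to be affected. In the least favourable case examined (mean 425 ms, reading SD 10 ms, the stricter limit for everyone) it is about one. A single affected value moves a visit mean by roughly half a millisecond or less. The reference to an outlier analysis is a clerical slip that analysts resolve by producing the listings and tables that 8.6.4 does specify. It can be tidied if the SAP is reopened for another reason.

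The sizes rest on assumed QTcF means and SDs, on independent readings, and on the schedule showing ECGs only at Screening and Check-in. The primary rosuvastatin comparison uses no ECG data and is unaffected in every case.
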